5.5.8. Efficacy Assessments

This section describes the efficacy assessments including how scores are calculated.

5.5.8.1. Percent Predicted Slow Vital Capacity

SVC is used to evaluate pulmonary status. It is the maximum volume of air that can be exhaled slowly after slow maximum inhalation. The percent predicted SVC presents the test result as a percent of the predicted values for patients based on sex, age, height, and race. It is calculated as: $\text{Percent Predicted SVC} = (\text{Trial SVC} / \text{Predicted SVC}) \times 100 (\%)$

The predicted SVC is calculated using the Quanjer GLI-2012 Regression Equation ([Quanjer 2012](#)) that factor the characteristics of sex, age, height and race into the prediction.

For male,

$$\begin{aligned} \text{Predicted SVC} = & \exp [-11.2281 + 2.4135 \times \ln(\text{Height})(\text{cm}) + 0.0865 \times \ln(\text{Age})(\text{yrs}) \\ & - 0.1684 \times \text{AfrAm} - 0.0405 \times \text{NEAsia} - 0.1177 \times \text{SEAsia} \end{aligned}$$

$$- 0.0825 \times \text{Other} + \text{Mspline}]$$

For female,

$$\begin{aligned} \text{Predicted SVC} = & \exp [-10.403 + 2.2633 \times \ln(\text{Height})(\text{cm}) + 0.0234 \times \ln(\text{Age})(\text{yrs}) \\ & - 0.1555 \times \text{AfrAm} - 0.0262 \times \text{NEAsia} - 0.1516 \times \text{SEAsia} \\ & - 0.0833 \times \text{Other} + \text{Mspline}] \end{aligned}$$

where

$\ln()$ = natural log transformation

AfrAm = 1 if a patient is African American, otherwise = 0

NEAsia = 1 if a patient is from North East Asia, otherwise = 0

SEAsia = 1 if a patient is from South East Asia, otherwise = 0

Other = 1 if a patient belongs to other ethnic group or has mixed ethnicity, otherwise = 0

Mspline is determined by age and sex as shown in [Appendix D](#).

For each clinical visit, a patient's SVC was evaluated in triplicate. The highest result among the evaluable measurements confirmed by the central read of an independent pulmonologist will be used for analysis (ie, measurements not confirmed as evaluable by the central read will be excluded from analysis). For SVCs measured at home, the highest result among the evaluable measurements collected during a day will be used for analysis, where 'evaluable' is defined as a measurement of SVC is not smaller than 0.5 times and not greater than 1.5 times of the highest evaluable SVC measured in clinic during the same week.

The percent predicted SVC declines over time in patients with ALS. The change from baseline in percent predicted SVC will be calculated as the post baseline value minus the baseline value, so that a negative number for change from baseline indicates respiratory function decline relative to baseline, and a positive treatment difference (reldesemtiv minus placebo) favors reldesemtiv.

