12. ALSAQ-5
13. Record Health Economic Outcomes Measures
14. AE/SAE evaluation and concomitant medication assessment (since last visit)
15. BDI-Fast Screen

Patients will receive their first dose of study drug (CK-2127107 or placebo) within 2 hours of a meal.

The following assessment will be performed after the first dose of study drug is given:

16. PK blood sample at 1 hour post-dose

Training will also be provided to the patient for the measurements patients will perform at home.

- For patients who have access to a mobile device, the application will be downloaded to the device and instructions provided as detailed in the study manual on recording voice.
- All patients will be trained in performing SVC using a portable spirometer (if the device is suitable for use in that region) as detailed in the study manual.

Home voice recordings and SVC testing will be performed by the patient weekly for the duration of the study following Day 1.

Patients will be given an adequate supply of study drug (CK-2127107 or placebo) to take twice daily for 4 weeks. A dosing diary will be provided for patients to record the date and time of twice daily study drug administration.

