7.9.2. Time-To-Event Analysis for Muscle Strength

Time-to-event analysis will be performed for muscles that had a measurable muscle strength at baseline. The muscle strength measured by HHD will be analyzed using proportional hazard Cox regression model. The event is defined as muscle strength as measured by HHD equals 0 from any muscle in the evaluated muscle groups. For patients who had the event, the date of muscle strength reached 0 will be used as the event date. For patients who did not have the event, data will be censored at their last date of study visit. Kaplan-Meier method will be used to summarize the time to event, and median, 95% CIs of the median, Q1, Q3, and range will be provided.

7.9.3. Evaluation of SVC Measured at Home Using SVC Measured in Clinic as the Standard

In addition to performing SVC assessments in clinic, GoSpiro home spirometer was given to patients for collecting their SVC data weekly from home. However, the usage of the spirometer varies among patients due to different reasons (eg, patients forgot to take the assessments or had technical difficulties, etc.). Hence it is of interest to evaluate consistency of the SVCs measured at home vs. the SVCs measured in clinic. Also, there may be potential learning effect due to more frequent use of the spirometer that may resulting in higher SVC assessed later on. The analyses to be used for the evaluations are described in the following sections.

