7.9.3.1. Correlation Between at Home and in Clinic Assessments of SVC

The test-retest reliability of SVC measured at home will be assessed using the measures in clinic as the standard for each patient. Each measure at home will be paired with a measure in the clinic within a seven-day of window. Correlation between at home and in clinic SVC assessments overall and by visit will be evaluated using Pearson correlation coefficient and paired t-test.

7.9.3.2. Change from Baseline to Week 12 in Percent Predicted SVC Assessed at Home and in Clinic

The SVC assessed at home and in clinic will be combined for a supportive analysis of change from baseline to Week 12 in percent predicted SVC. A MMRM will be used for the analysis. The response variable will be the change from baseline to each post baseline visit up to Week 12. The model will include the following covariates:

- Treatment (reldesemtiv 300 mg/day, 600 mg/day and 900 mg/day, and placebo)
- Location of SVC collection (at home or in clinic)
- Baseline (baseline value of the response variable)
- Pooled site
- Time (time from the first dose, a continuous variable)
- Riluzole and edaravone use status at baseline
- Baseline-by-time interaction
- Treatment-by-time interaction

An unstructured variance-covariance structure will be used to model the within-subject errors. If a model fails to converge, other covariance matrix structures (eg, compound symmetry) may be used instead of the unstructured covariance matrix. Least square means and the corresponding standard errors, 95% CIs and p-values will be presented.

7.9.3.3. Time to Event Analysis of Percent Predicted SVC Decline to Less Than 50%

To evaluate consistency of the SVCs measured at home vs. that measured in clinic, percent predicted SVC collected during clinic visits and at home will be analyzed using a proportional hazard Cox regression model. The event is defined as percent predicted SVC decline to less than 50% during the 12 weeks of the study. For patients who had the event, the first date of SVC less than 50% will be used as the event date. For patients who did not have the event, data will be censored at their date of study visit or Week 12 visit, whichever is earlier. Kaplan-Meier method will be used to summarize the time to event for percent predicted SVC measured in clinic and at home, separately. The median of the time to event, 95% CIs of the median, Q1, Q3, and range will be provided.

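### Home SVC readings are screened against the same clinic value that SAP 7.9.3.1 then uses to judge them, so correlation is biased upward and the spread of differences downward, by an amount the documents do not fix

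*SAP*

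**What the plan says.** SAP 5.5.8.1 defines the home SVC value: "the highest result among the evaluable measurements collected during a day will be used for analysis". A reading is evaluable if it is "not smaller than 0.5 times and not greater than 1.5 times of the highest evaluable SVC measured in clinic during the same week". Clinic readings in the same section are screened differently, by an independent pulmonologist's central read: "measurements not confirmed as evaluable by the central read will be excluded from analysis".

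SAP 7.9.3 gives the purpose of the home-clinic comparison: "Hence it is of interest to evaluate consistency of the SVCs measured at home vs. the SVCs measured in clinic". SAP 7.9.3.1 sets the method: "The test-retest reliability of SVC measured at home will be assessed using the measures in clinic as the standard for each patient". On pairing it says "Each measure at home will be paired with a measure in the clinic within a seven-day of window", and on statistics "Correlation between at home and in clinic SVC assessments overall and by visit will be evaluated using Pearson correlation coefficient and paired t-test".

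SAP 7.9.3.1 does not say whether the screen in 5.5.8.1 applies. It provides no unscreened analysis and no count of readings removed. Home testing is weekly (Protocol 5.2).

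**The concern.** The rule for keeping a home reading is closeness to the clinic reading, and the question then asked is how close home readings are to clinic readings. A partial blow, a leak or a double-counted breath that puts a reading outside the band is evidence about the home device, yet it is removed before the device is assessed. The clinic screen does not have this problem, because it does not refer to the home value.

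At stake is how the sponsor describes home spirometry. Home SVC is a named exploratory objective and supplies two exploratory endpoints (change and slope). It is also pooled with clinic SVC in a supportive model (SAP 7.9.3.2). The agreement result is the plan's own evidence on whether those home data can be trusted.

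**Working it through.** **Stated figure.** The documents give no expected correlation, home error SD or discard rate, so there is no plan figure to reproduce.

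**What follows from the rule alone.** Let C be the clinic SVC, H the home SVC and R = H/C. A reading is kept only if 0.5 ≤ R ≤ 1.5, so every kept difference satisfies -0.5C ≤ H - C ≤ +0.5C, whatever the device does. At an assumed C of 3.2 L, no kept difference can exceed 0.5 × 3.2 = 1.6 L in either direction.

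**Size under assumed inputs.** All of the following are assumptions. C is lognormal with CV 30%. A good reading is C with 7-10% error. A failed reading is 10-60% of C (low) or 140-200% of C (high). The screen is applied to each reading, the highest kept reading of the day is taken, and Pearson r is compared with the r obtained from the highest of all readings.

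| Assumed failures | Readings per day | r, no screen | r, screened |
|---|---|---|---|
| 5%, all low or half high | 1 | 0.84-0.87 | 0.93-0.96 |
| 10%, all low or half high | 1 | 0.77-0.79 | 0.92-0.95 |
| 20%, all low or half high | 1 | 0.66-0.67 | 0.90-0.93 |
| 5%, isolated, low | 3 | 0.970-0.984 | 0.970-0.985 |
| 10%, isolated, low | 3 | 0.967-0.982 | 0.968-0.983 |
| 20%, isolated, low | 3 | 0.950-0.968 | 0.959-0.976 |
| 10%, isolated, half high | 3 | about 0.81 | 0.95-0.97 |
| 10%, whole session low (7% error) | 3 | about 0.84 | about 0.92 |

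With one reading per day and 10% failures, the SD of the percent difference falls from 21-24% to 9-12%.

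The pattern has a simple explanation. With three readings and isolated low blows, the daily maximum has already discarded the bad reading, so the screen adds at most about 0.01 to r. The maximum gives no protection when every reading in the session is low, and when a reading is falsely high the maximum selects it.

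**Second set of assumptions.** Clinic SVC has mean 3.2 L and SD 0.7-1.0 L, home log-SD is 0.10-0.35, 0-15% of sessions are faulty, and there are one or three readings per day, giving 72 scenarios. The screen left r unchanged or raised it in all 72, by between 0 and about 0.35. The SD of differences stayed the same or shrank. With log-SD 0.10 and no faulty sessions, r was 0.89 both ways and about 0% of readings were lost. With log-SD 0.20, one reading and no faulty sessions, r went from 0.71 to 0.74 and 2% were lost.

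**Paired t-test.** The statistic is the mean difference divided by SD/√n. The screen moved the mean difference from 0.13 to 0.00 L in one scenario and from -0.02 to +0.20 L in another. With single readings and 10% partial blows it moved from -6.5% to -1.0% of the clinic value, which would hide under-reading. Because the SD in the denominator shrinks as well, the t statistic has no fixed direction.

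**Limiting case, for mechanism only.** If home readings were unrelated to clinic readings (true r = 0), the screen alone would give r of about 0.27, 0.38 and 0.46 at between-patient CV 25%, 30% and 35%.

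**The case against.** The strongest reply has four parts.

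1. *The screen may not apply.* SAP 7.9.3.1 speaks of each home measure, not each evaluable one, so all readings could be meant. This stands as an ambiguity. But 5.5.8.1 contains the only definition of a home SVC value for analysis and states no exception, so the screened reading is the likelier one. If the other was intended, one sentence would settle it.

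2. *A band of ±50% is an ordinary gross-error screen, and the daily maximum does most of the work.* This stands for a device with about 10% error and no gross failures, and for isolated low blows among several readings. The documents do not say how many home readings are taken per day, so that protection cannot be assumed. If there are no gross failures the screen is also unnecessary here; it alters the result only where failures exist.

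3. *A reader might infer that every agreement statistic is inflated.* The documents do not support this. The plan names two statistics, and only for the correlation is the direction of bias predictable. The paired t-test can look better or worse.

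4. *A reader might infer that a poor device would pass, or that the trial's conclusion is at risk.* SAP 7.9.3 sets no pass threshold, sits under Exploratory Analyses and is outside the testing sequence in SAP 7.4. The primary analysis uses clinic SVC confirmed by the central read (SAP 7.5.1). The unrelated-device case shows how the mechanism works; it is not a plausible spirometer.

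A count of excluded readings may also exist in the table shells mentioned in SAP 5.3, which are not part of these documents.

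**Conclusion.** The concern holds within limits. As SAP 5.5.8.1 and 7.9.3.1 most naturally read together, selection depends on the quantity being assessed. The correlation is then biased upward and the spread of differences downward; the paired mean difference is distorted in an unpredictable direction.

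The size cannot be derived from the documents. Under the assumed inputs it runs from nothing (about 10% error with no gross failures) or about 0.01 in r (isolated low blows with a daily maximum of three) to a material shift at 10% failures: r of about 0.78-0.84 unscreened against 0.92-0.96 screened, when one reading is taken, whole sessions fail or some failures read high. Which case applies depends on the failure rate, the failure direction and the number of readings per day, none of which is stated.

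The consequence is confined to the exploratory evaluation of home SVC. It is worth correcting because the correction is cheap, not because the primary result depends on it.

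**What to change.** In SAP 7.9.3.1:

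- State that the agreement analysis uses the highest recorded home reading of the day, without the 0.5-1.5 clinic-ratio screen.
- Show the result on screened readings as secondary.
- Tabulate, by visit and dose group, the number and percentage of home readings that fail the 0.5-1.5 rule, split into low and high.

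The screen may stay for the home-SVC change and slope endpoints, where the clinic value is not the yardstick.

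The cost is one or two sentences and one extra table, with no new data. The downside is that reported agreement may look worse and will be more sensitive to outliers; showing both results side by side, with the counts, lets a reader see how much a few readings matter.

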5.5.8.2. Amyotrophic Lateral Sclerosis Functional Rating Scale-Revised

The ALSFRS-R is a validated rating instrument for monitoring the progression of disability in patients with ALS ([Cedarbaum 1999](#)). The assessment is based on 12 clinical ratings that are categorized in four domains: bulbar (speech, salivation, swallowing), fine motor skills (handwriting, cutting food and handling utensils, dressing hygiene), gross motor skills (turning in bed and adjusting bedclothes, walking, climbing stairs) and respiratory function (dyspnea, orthopnea, respiratory insufficiency). Each clinical rating is assessed using an ordinal scale that ranges from 0 to 4, with a score of 4 representing normal function and lower scores indicating worse function.

The ALSFRS-R total score is calculated as the sum of the 12 ratings. The score of each of the four domains (bulbar, fine motor skill, gross motor skill, and respiratory function) is calculated as the sum of the three ratings within each domain, and can range from 0 to 12. If a single rating is missing, the score of the corresponding domain and the ALSFRS-R total score will be set to missing.

The ALSFRS-R total scores can range from 0 to 48, with higher scores indicating less functional impairment. The score change from baseline will be calculated as the post baseline score minus the baseline score, so that a negative number for change from baseline indicates greater impairment relative to baseline. A positive treatment difference in the change from baseline (reldesemtiv minus placebo) favors reldesemtiv.

5.5.8.3. Muscle Strength Mega Score

Patients' muscle strength was measured bilaterally using HHD and hand grip dynamometry. The HHD measures muscle strength of the six muscle groups: elbow flexion, wrist extension, first dorsal interosseous, knee extension, ankle dorsiflexion, and hip flexor. The hand grip dynamometry measures maximum hand grip strength. In each clinical visit, a patient's muscle strength was evaluated in triplicate for those measured by HHD. The maximum result among the three measurements will be used for analysis.

The muscle strength was recorded as 0 (pounds) on the eCRF for the following situations:

- A patient was able to assume the correct position but unable to exert any force.
- A patient was unable to assume the correct position, and the evaluator is able to determine the cause as muscle weakness or contracture.
- A patient was too weak to perform the test.

The muscle strength of each measured body location is transformed as a percent change from baseline using the equation: $[(\text{post baseline value} - \text{baseline value}) / \text{baseline value}] \times 100$. The transformed muscle strength will be set to missing if the baseline value is zero.

The mega score is a composite score that averages strength across muscle groups. It is calculated as the mean of the non-missing transformed muscle strength scores among the 14 measured body locations, including the six muscle groups measured bilaterally by the HHD, and the hand grip strength measured bilaterally by hand grip dynamometry.

A greater muscle strength mega score indicates less muscle strength loss, and a positive treatment difference (reldesemtiv minus placebo) favors reldesemtiv.

5.5.8.4. Ashworth Score

Ashworth score measures resistance during passive soft-tissue stretching and is used as a simple measure of spasticity (Bohannon 1987). Ashworth score will be assessed for elbow and knee bilaterally in this study. For analysis purpose, the average of non-missing measurements from all assessed body location will be calculated as the Ashworth total score.

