8.3.2. Safety Endpoints

The safety endpoints are listed in the following:

- The incidence and severity of TEAEs
- Clinically important changes in safety assessment results [including, as appropriate, vital signs, clinical laboratory tests, ECGs, Ashworth score, falls assessment, physical and neurological examinations, BDI-Fast Screen and suicidality assessment].

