8.4.5.8. Ashworth Score

Ashworth score will be determined bilaterally at the elbows and knees with the results summarized at each body location.

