8.9. Ashworth Score

Ashworth score will be assessed at all study visits. Summary statistics of the Ashworth total score at each study visit will be tabulated. A list will be provided with the actual assessment date and answers to all the questions.

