12. CHANGES TO ANALYSES SPECIFIED IN PROTOCOL

Not available.

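### The protocol asks for Ashworth results joint by joint; the SAP tabulates only an average over whichever joints were scored, and records no departure

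*SAP*

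**What the plan says.** Protocol 8.4.5.8 sets the reporting rule: "Ashworth score will be determined bilaterally at the elbows and knees with the results summarized at each body location". Protocol 8.3.2 places the scale among the safety endpoints, which are worded as "Clinically important changes in safety assessment results [including, as appropriate, vital signs, clinical laboratory tests, ECGs, Ashworth score, falls assessment" and further items. Protocol 8.4.5 has safety data summarised by dose group.

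The SAP keeps the same four locations (5.5.8.4: "Ashworth score will be assessed for elbow and knee bilaterally in this study"). For analysis, however, it reduces them to one number: "the average of non-missing measurements from all assessed body location will be calculated as the Ashworth total score". SAP 8.9 then gives two outputs. The table is "Summary statistics of the Ashworth total score at each study visit will be tabulated". The listing is "A list will be provided with the actual assessment date and answers to all the questions". Neither section sets a minimum number of assessed joints, and 8.9 does not mention change from baseline.

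The whole content of SAP 12, on changes from the protocol's analyses, is "Not available".

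**The concern.** A patient-level listing is not a summary, so the SAP as written does not deliver what the protocol committed to, and nothing in the SAP says that the commitment was dropped. Protocol 8.7 expects changes in method described in the SAP to reach the study report. An unrecorded change is easily missed at that step.

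The table matters more here than its descriptive status suggests, for two reasons.

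- Muscle spasticity is on the list of expected signs of ALS progression (Protocol 7.4.3, Table 5). Under Protocol 7.3.1, such signs are not collected as adverse events unless they are serious. The AE tables can therefore under-capture non-serious spasticity that is attributed to progression.
- The Ashworth scale is the only direct spasticity measure scheduled at every visit (Protocol 5.13.9 and Appendix A). A patient who completes treatment has neurological examinations only at Screening and at Follow-Up, four weeks after the last dose.

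If the main Ashworth table shows only an average, a worsening confined to one joint or one region appears small. A change in which joints were scored can also look like a change in spasticity.

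**Working it through.** The documents give no Ashworth figure to reproduce. The check is a comparison of texts, followed by arithmetic on illustrative grades.

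**Texts side by side**

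- Locations: four in both documents (elbow and knee, left and right).
- Summary owed by the protocol: results at each location (8.4.5.8), by dose group (8.4.5).
- Summary specified in the SAP: one average per patient (5.5.8.4), tabulated by visit (8.9), with dose level supplied by the general rule in SAP 5.1.
- Joint-level output in the SAP: a listing only (8.9). No other section of the SAP specifies a by-location table.
- Departure recorded: none (SAP 12).

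**Dilution.** With all four joints assessed, the average is (g1 + g2 + g3 + g4)/4, so a change of k grades at one joint moves it by k/4. Starting from 1, 1, 1, 1:

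- One joint up by 1: (2 + 1 + 1 + 1)/4 - 1 = +0.25. A by-joint row would show +1 at that joint.
- One joint up by 2: (3 + 1 + 1 + 1)/4 - 1 = +0.50. A by-joint row would show +2.
- One joint up by 1 and another down by 1: (2 + 0 + 1 + 1)/4 - 1 = 0. By-joint rows would show +1 and -1.

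**Missing joint.** The rule averages raw grades over the joints present, so the baseline and later averages can rest on different joints.

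- Baseline 3, 1, 1, 1 averages 6/4 = 1.50. Nothing changes, but the joint graded 3 is not assessed later: 3/3 = 1.00. The apparent change is -0.50, although the true change is 0.
- Baseline 3, 1, 1, 0 averages 5/4 = 1.25. Later the joint graded 3 is not assessed and one joint goes from 1 to 2: (2 + 1 + 0)/3 = 1.00. The apparent change is -0.25. With all joints assessed it would be (3 + 2 + 1 + 0)/4 - 1.25 = +0.25, so the sign is reversed.
- If only joints present at both times are used, the first case gives 3/3 - 3/3 = 0. The second gives 3/3 - 2/3 = +0.33. Both then point the right way.

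**How the SAP treats its other composites.** ALSFRS-R (5.5.8.2), ALSAQ-5 (5.5.8.7) and BDI (5.5.10.5) totals are set to missing if any item is missing. The muscle strength mega score (5.5.8.3) also averages what is available, but it averages each location's own percent change from baseline. A dropped location there does not shift the result through its baseline level. The Ashworth average has neither protection.

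**The case against.** The conflict between the texts is hard to dispute. The objections go to how much it matters.

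- **No data are lost.** The listing keeps the joint-level answers, serious spasticity is still recorded as an SAE, and falls are tabulated with injury and preceding symptoms (SAP 8.11). This stands, and it limits the point to a missing summary.
- **Unseen shells might hold a by-location table.** SAP 5.3 refers to table shells, and 8.9 does not say that the average is the only table. This is possible, but the SAP text is the specification and it names the average as the analysis variable.
- **Missing joints and cancellation are constructed cases.** This is fair. The scale is scheduled at every visit, and nothing in the documents suggests that joints will often be missed. Dilution is certain whenever only some joints worsen. Full cancellation needs opposite changes at different joints, and a false change needs a missing joint.
- **The average can be the better summary.** This is also fair. A reader might infer that averaging multiplies the number of patients needed to detect a spasticity effect. The documents do not support a figure of that kind. Ashworth has no planned test or power target, and the answer depends on assumptions found nowhere in the plan. With equal variances, an assumed between-joint correlation r of 0.2 to 0.5 and an effect at the knees only, the four-joint average needs 1 + 3r = 1.6 to 2.5 times the patients that a single-knee row needs. If all four joints shift equally, the advantage reverses: a single joint needs 4/(1 + 3r) = 2.5 to 1.6 times what the average needs. The drug is oral and acts on fast skeletal muscle generally, so a diffuse effect is at least as arguable.
- **The protocol asks for less than a full set of tables.** Its Ashworth section requires a summary by location. It does not itself ask for change from baseline, by-visit display or a count of patients who worsened. This stands, and the fix separates what is owed from what is advisable.

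**Conclusion.** The SAP does not specify the by-location Ashworth summary that the protocol requires, and it does not record the departure. This should be corrected before database lock.

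The size is modest. A one-grade change at a single joint appears as 0.25 in the average, and under the non-missing rule an unassessed joint can produce a spurious shift, -0.50 in the example. The 0.25 follows from having four locations. The missing-joint figures rest on illustrative grades, and the plan gives no basis for saying how often such cases would arise.

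Two stronger readings should be resisted. One is that a spasticity signal would be lost altogether. The documents do not support that, because joint-level data are listed and serious spasticity is reported as an SAE. The other is that the trial's conclusions are at risk. Ashworth is a descriptive safety summary and enters none of the primary or secondary efficacy analyses.

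**What to change.** In SAP 8.9:

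1. Add a summary at each elbow and each knee by dose group. This is what the protocol requires.
2. Show it by visit with change from baseline, in line with the laboratory, vital-sign and ECG summaries in SAP 8.4 to 8.6. This is a matter of consistency, not a protocol requirement.
3. Keep the average as a supplementary measure, and compute its change only over joints assessed at both baseline and the visit in question.
4. Optionally, add the number and percentage of patients with a rise of at least one grade at any joint.

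If the sponsor prefers the average to stand alone, SAP 12 should record and justify that.

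The cost is one extra descriptive table from data already collected, plus one sentence in SAP 5.5.8.4 for the missing-joint rule. The optional count would add a few rows.
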